3.6 Tertiary Endpoints*

- i. 14-day delirium and coma free days
- ii. Incidence of ICU acquired weakness (MMST and hand grip strength dynamometry and maximal inspiratory pressure) at day 7 and ICU discharge
- iii. Health-related quality of life, (EQ-5D-5L) at 90 days and 180 days
- iv. Hospital Anxiety and Depression Scale (HADS) at 90 days and 180 days
- v. Social and Wellbeing (SF-36) at 90 days and 180 days
- vi. Impact of Events Scale (6 item) at 90 days and 180 days
- vii. Care and wellbeing needs at 90 days and 180 days
- viii. Cognitive function (MoCA) at 90 days and 180 days

4. STUDY DESIGN

Participants will be recruited from multiple sites internationally. The PANTHER platform will use a Bayesian Adaptive Multi-Arm Trial design, which can be viewed as an extension of a Multi-Arm Multi-Stage (MAMS) design.

The platform will recruit patients in hospital and who are critically ill with different clinical syndromes. Initially the target population will be patients with ARDS. Over time other clinical syndromes may be added; in particular, the platform will prepare to include patients with pandemic infection. Patients will be stratified into different subphenotype strata prior to randomisation. Initially, the strata will be the hyper and hypoinflammatory subphenotypes described in ARDS. The regular adaptive analyses will enable us to efficiently identify differential treatment responses across subphenotypes by examining treatment effect within subphenotype strata and stopping interventions in each subphenotype where there is evidence of futility or efficacy. The design allows additional new interventions and subphenotypes to be added over time.

Design and planning for the addition of new interventions and subphenotypes will continue as the platform trial is ongoing.

Confidential Page 17 of 48

^{*}Not all sites are expected to collect these endpoints

[figure not shown]
4.1 Design

A multicentre, allocation concealed, randomised, open-label Bayesian adaptive multi-arm platform trial with pre-defined triggers for efficacy and futility stopping (as compared to usual care). Randomisation will be balanced with equal ratios between usual care and each intervention participants are eligible for, i.e. a 1:1 ratio (usual care versus intervention (where eligible) by subphenotype). There is no fixed sample size, but we have capped the sample size for the initial treatments and subphenotype. We will recruit a maximum of 529 per active intervention in the hyperinflammatory subphenotype, and 504 per active intervention in the hypoinflammatory subphenotype. See the statistical design appendix for more information for how this sample size was derived.

Figure 1: Indicative study flow chart demonstrating study design by initial precision medicine subphenotype

Bayesian Adaptive Multi-Arm Trial design

Up to 2 active treatments recruiting in each subphenotype at any time

5. PARTICIPANT ENTRY

5.1 Study setting and population

The population to be included into the platform will be critically ill patients in hospital (46).

Platform level inclusion criteria

- 1. Critically ill patients in hospital and at least 1 of the following: -
 - a) Acute respiratory distress syndrome (ARDS)*
 - b) A pandemic associated syndrome (this will be triggered if a new pandemic is declared)
- *ARDS as defined by:-
- (i) a known acute clinical insult or new or worsening respiratory dysfunction, and

Confidential Page 18 of 48

	Protocol No: 175151	Sponsor:	Imperial	College	V 2.1 30.07.2025
		London			
PANTHER					

(ii) receiving respiratory support via invasive mechanical ventilation or non-invasive ventilation including continuous positive airway pressure, or high-flow nasal oxygen ≥30L/min and

(iii) Within the same 24-hour time period:

- bilateral opacities on chest imaging not fully explained by effusions, lobar/lung collapse/atelectasis, or nodules, and
- respiratory failure not fully explained by cardiac failure, fluid overload, pulmonary embolism, acute airways disease, or interstitial lung disease and
- PaO2/FiO2 ratio <40 kPa from arterial blood gases, or SpO2/FiO2 <315 from pulse oximetry where SpO2 <97.

The time of onset of ARDS is when the last criterion in (iii) is met.

Platform level exclusion criteria

- (a) >48 hours from diagnosis of ARDS
- (b) Planned withdrawal of life-sustaining treatment within the next 24 hours
- (c) Previous enrolment in the PANTHER trial in the last 12 months
- (d) Declined consent

Additional intervention-specific inclusion / exclusion criteria

These are given in the intervention specific appendices

6. PROCEDURES AND MEASUREMENTS

6.1 Identification and recruitment of participants

Patients will be identified by local clinical and clinical research staff employed in the recruiting hospitals. Patients screened and who meet inclusion criteria who are not recruited on to the study will be documented, including the reason(s) for not being enrolled on the study.

6.2 Screening and pre-randomisation evaluations

[figure not shown]
The screening will be conducted by local clinical and clinical research staff employed in the recruiting hospitals using the routinely clinically collected data.

Subphenotyping will be undertaken when the patient meets the criteria for inclusion in the trial and the appropriate consent process has been followed. Measurement of the biomarkers to determine subphenotype will take place in real time, prior to randomisation. Details about the subphenotyping process are included in the subphenotype appendix.

6.3 Randomisation and Blinding

The trial is open-label whereby participants, the clinical team and study team will not be masked to the interventions. To avoid bias during the ongoing PANTHER platform, where possible, modifications will be made. Only the unblinded trial statisticians will have access to emerging aggregate data and results by treatment allocation until interventions are stopped. These statisticians will be responsible for carrying out the adaptive analyses and construction of all statistical reports for regular DMC meetings.

Confidential Page 19 of 48

Each participant will be assigned a unique trial ID which is linked to their treatment allocation.

Bias will be minimised by the following:

Detection and performance: The primary outcome and most of the secondary outcomes are objective outcomes that will be unaffected by knowledge of treatment allocation. The unblinded trial statistician undertaking the planned adaptive analyses will not be involved in design decisions of the ongoing platform. Delivery of usual care based on international guidelines will decrease the likelihood of performance bias. No aggregate data by intervention will be available to the study team throughout the trial prior to any statistical trigger being met and final analysis.

Selection bias: Treatment allocation will be concealed prior to randomisation using an automated online system. To ensure clinicians have equipoise, we will evaluate screening logs and examine reasons why patients have not been enrolled into the study.

Attrition bias: The primary outcome along with most other outcome data will be collected during the hospital stay. Data on mortality will be derived electronically from routinely collected health data sources where possible. Experience from previous trials indicates missing outcome data for the primary outcome and mortality to day 90 will be minimal both in the UK and at international sites. Withdrawal rates are typically <5% in critical care trials (10,11). We will seek participants' (or their representatives'), permission to retain data collected up until the time-point that they choose to withdraw. This will maximise primary and secondary outcome data acquisition. Our experience in the UK and internationally is that patients normally agree to proceed on this basis.

Reporting bias: Source data verification (from clinical records and hospital computer records as described in the trial monitoring plan) will be used to minimise the risk of reporting bias. The main clinical outcomes of this study (e.g., death, organ support, duration of stay, and serious adverse events) are recorded contemporaneously on participant clinical records.

Treatment fidelity and contamination due to crossover: As the interventions are prescribed and then administered by nurses as part of routine ICU clinical care there is minimal risk that treatment will not be administered. As the interventions likely to be included are not recommended as part of usual care there is also minimal risk of unplanned crossovers within the interventions. In the event of cross-over occurring at a site, the site will be re-trained and if this occurs repeatedly the site will be closed to recruitment.

Randomisation

Allocation to treatment interventions will be via a minimisation algorithm which enables dynamic allocation based on the distribution of recruited participants, allocating participants to the treatment that mainsubtains balance in participant characteristics. To avoid allocations being completely deterministic, we will include random allocation in between 10-20% of cases to ensure unpredictability of individual allocations. This will result in approximately 5-10% of individuals not being allocated to the treatment that minimises imbalance in participant characteristics between treatments. The minimisation algorithm will be applied within subphenotypes separately. Minimisation will then be by country and intervention eligibility. Allocation will be conducted through an online password protected data system

Confidential Page 20 of 48

London

managed centrally by Imperial Clinical Trials Unit who are the data coordinating centre for the platform trial. The algorithm will be updated when subphenotype, countries or interventions change.

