At the first adaptive analysis, confirmation of the validity of the proportional odds assumption will be carried out in each subphenotype. This will be based on the observed distribution of the primary outcome ordinal scale in each treatment intervention compared to usual care. If the proportional odds assumption is not met, then alternative categorisations (i.e. grouping some categories in the ordinal scale together) will be explored. For all adaptive analysis we will examine the consistency of the unadjusted between-group treatment effect across the composite outcome elements (death and organ support free days) for each comparison within each subphenotype.

Very little missing data are expected for the primary outcome; we anticipate minimal loss to follow-up, and eCRFs will be designed so that recording of primary outcome data is mandatory. If the level of missingness does not exceed 5% then the missing data will be assumed to be ignorable, i.e. a complete case analysis will be carried out. If over 5% of outcome data are missing, then the missingness pattern and relationship to other variables will be explored and multiple imputation will be performed.

Statistical stopping triggers

The criteria for stopping recruitment to a treatment group within either subphenotype are based on the probability that the unadjusted odds ratio crosses a predefined value by a predetermined probability threshold. The initial triggers for stopping were identified through extensive simulations to optimise the trial operating characteristics and achieve an appropriate balance between the sample size needed, maximising the power to graduate treatments exceeding the minimal clinically important effect and minimising the chance of graduating treatments with no effect (type I error).

Stopping recruitment to a treatment within either subphenotype will be considered if any of the following conditions are met at any adaptive analysis:

- For efficacy if there is at least an 84% probability of the proportional odds ratio exceeding 1.1.
- For futility if there is at least a 78% probability of the proportional odds ratio falling below 1.075.

These are considered non-binding stopping rules as the DMC will also take into consideration information presented on other outcomes including safety and recruitment data.

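### Minimisation leaves baseline ventilation unbalanced while the stopping triggers use an unadjusted odds ratio: avoidable noise, not bias, and cheap to remove

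*Protocol*

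**What the plan says.** - **Allocation (Protocol 6.3).** The stated aim is "allocating participants to the treatment that mainsubtains balance in participant characteristics". On structure: "The minimisation algorithm will be applied within subphenotypes separately", and "Minimisation will then be by country and intervention eligibility". The algorithm is to be updated when subphenotypes, countries or interventions change.
- **Entry (5.1).** Criterion "ii) receiving respiratory support via invasive mechanical ventilation or non-invasive" ventilation (CPAP included), or high-flow oxygen at 30 L/min or more.
- **Endpoint (3.4).** Organ support-free days to day 28, with death scored worst. High-flow oxygen counts as support only at FiO2 of 0.4 or more.
- **Triggers (9.4).** These are "based on the probability that the unadjusted odds ratio crosses a predefined value by a predetermined probability threshold". The two rules are "For efficacy if there is at least an 84% probability of the proportional odds ratio exceeding 1.1" and "For futility if there is at least a 78% probability of the proportional odds ratio falling below 1.075". The first look is at 240 participants in the subphenotype, 80 per arm.
- **Safeguards.** Baseline characteristics are summarised by group at adaptive analyses (9.4). The triggers are non-binding (9.4). Unadjusted and adjusted effects appear in all reports, and the final analysis adjusts for minimisation covariates and other strong prognostic variables (9.6).

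**The concern.** Baseline respiratory support is tied to the endpoint by definition. An intubated entrant starts with support to come off. By contrast, an entrant on high-flow oxygen at FiO2 0.31 with SpO2 96 meets the SpO2/FiO2 limit of 315 (96/0.31 = 310). Without a vasopressor or inotrope, that patient starts the trial already free of organ support as 3.4 defines it. The variable is known before randomisation because it is an entry criterion.

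It is nevertheless left to chance within each subphenotype, and the statistic that triggers stopping or graduation does not adjust for it. Early looks matter in this design: the expected mean sizes are 120 and 82 per intervention. At stake is a modest amount of noise in decisions taken at small numbers, and a possible conflict between an unadjusted trigger and the adjusted final result.

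**Working it through.** **Inputs from the protocol.** First look at 80 per arm; triggers as quoted; looks every 3 months (hypoinflammatory) or 6 months (hyperinflammatory); 70:30 mix; up to 70 sites at one patient per month; cap 504 (hypoinflammatory); effect sizes POR 1.4 and 1.3.

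**Assumptions, not in the protocol.** 50-70% invasively ventilated at entry; POR 2-4 between ventilated and not; 1 - Σp³ of 0.85-0.95 for the outcome categories; flat prior; three arms; five hyperinflammatory looks.

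**1. The plan's own figures.** Var(log POR) = 6/[n(1 - Σp³)], n per arm. Hypoinflammatory looks fall at 80, then every 70 × 0.7 × 3/3 = 49 per arm, up to 504. Hyperinflammatory looks fall at 80, then every 70 × 0.3 × 6/3 = 42 per arm. With 1 - Σp³ = 0.95 and 400,000 runs:
- Hypoinflammatory: type I error 18.0-18.8% (futility acted on or ignored) against the stated 17-19%; power about 90-94% against 92-96%.
- Hyperinflammatory: about 16% against 18%; power about 65-66% against 70-71%.

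This is close enough for measuring differences. It is not an exact check, because the outcome distribution, prior and look schedule are left to the Statistical Design Appendix.

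**2. Size of chance imbalance at 80 per arm.** SD of the difference = √[2p(1 - p)/80].
- p = 0.5: 7.9 points; P(gap > 10 points) = 21%.
- p = 0.7: 7.2 points; P(gap > 10 points) = 17%.

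**3. Share of outcome variance.** R² = p(1 - p)(ln OR)² / [π²/3 + p(1 - p)(ln OR)²].
- OR 2: 0.120/(3.290 + 0.120) = 0.035 at p = 0.5; 0.030 at p = 0.7.
- OR 4: 0.480/(3.290 + 0.480) = 0.127 at p = 0.5; 0.109 at p = 0.7.

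**4. Effect of one 10-point gap.** It shifts log POR by about 0.10 × ln 2 = 0.07 to 0.10 × ln 4 = 0.14, a factor of about 1.07-1.15. At 80 per arm with 1 - Σp³ = 0.9, SE = √(6/72) = 0.289. Efficacy then needs an observed POR of 1.1 × exp(0.994 × 0.289) = 1.47, and futility 1.075 × exp(-0.772 × 0.289) = 0.86. The shift is 0.24-0.48 SE.

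**5. Effect of balancing, trigger still unadjusted.** Set-up of step 1, futility acted on. The estimator's true variance is multiplied by (1 - R²) and the model's posterior is left unchanged.

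| R² balanced | Hypo type I | Hypo power | Hyper type I | Hyper power |
|---|---|---|---|---|
| 0 | 18.0% | 90.1% | 16.2% | 65.3% |
| 0.03 | 17.4% | 90.5% | 15.6% | 65.3% |
| 0.08 | 16.4% | 91.2% | 14.9% | 65.3% |
| 0.12 | 15.5% | 91.7% | 13.9% | 65.2% |

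Type I error falls by 0.6 to 2.5 points (hypoinflammatory) and 0.6 to 2.3 (hyperinflammatory). About half of the false graduations occur at the first look (9.2 of 18.0; 9.1 of 16.2).

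**6. Balance against adjustment, first look only.** Six-category proportional odds model, 80 per arm, 50% ventilated, prognostic OR 0.6 / 0.4 / 0.25, 4,000 runs each.

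| Efficacy trigger | Unadjusted | Adjusted |
|---|---|---|
| POR 1, all trials | 8.5 / 9.6 / 9.9% | 8.6 / 9.6 / 9.8% |
| POR 1, gap ≥ 10 points favouring active (about 10% of trials) | 12 / 18 / 25% | 8 / 9 / 10% |
| POR 1.4, all trials | 44.7 / 42.5 / 41.5% | 45.1 / 44.9 / 44.7% |
| POR 1.4, same gap against active | 32 / 26 / 19% | 42-44% |

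Exact balance without adjustment (OR 0.4) gives a false trigger of 8.4% rather than 9.6%, and power of 42.7% rather than 42.5%. Balance therefore trims false triggers, while adjustment recovers power. Monte Carlo error is about 0.5-0.8 point over all trials and 1.5-2.5 points in the imbalance subsets.

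**The case against.** The strongest reply is that nothing is misstated, and four parts of it stand.

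- **Patient-level balance exists.** Minimisation runs within subphenotype, a patient-level stratum for which the design uses separate outcome distributions, and eligibility is also patient-level. A reader might infer that no patient prognostic factor is balanced, or that 6.3 contradicts its own aim. Neither is supported; what is missing is a respiratory-support or severity factor.
- **Imbalance is not extra error.** It belongs to the sampling variance of the unadjusted estimate, so it is inside the stated type I error. Step 6 shows the same overall false-trigger rate with and without adjustment. The large contrasts appear only after conditioning on an imbalance.
- **Safeguards exist.** The DMC sees baseline tables and adjusted effects, and is not bound by the trigger. The imbalance enters the trigger statistic, not automatically the decision.
- **The shift must be judged on the right scale.** It is tempting to set 1.07-1.15 beside the trigger values 1.1 and 1.075 and call it decisive. The observed POR needed at 80 per arm is about 1.47 or 0.86, so the shift is a fraction of one SE, and imbalance shrinks at later looks.

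Two parts do not dispose of the point. The formal trigger and the quoted operating characteristics still concern the unadjusted POR, and the protocol gives no rule for when unadjusted and adjusted results disagree. Nor is the gain zero: even at R² = 0.03 balancing lowers type I error at no cost in power.

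**Conclusion.** The point holds as a modest design improvement. Balancing baseline invasive ventilation would lower type I error by about 0.6 points (R² 0.03) to about 2.4 points (R² 0.12) in each subphenotype. Power is unchanged in the hyperinflammatory subphenotype and about 0.4 to 1.5 points higher in the hypoinflammatory one. The type I gain arises because the unadjusted posterior stays as wide as if the factor were unbalanced, so the trigger becomes slightly conservative.

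The sizes depend on the assumed 50-70% prevalence, prognostic POR of 2-4, outcome spread, flat prior and look schedule. A reader might infer biased decisions or an understated type I error; the documents support neither. Priority: optional to modest.

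**What to change.** At the next algorithm update, add invasive mechanical ventilation at randomisation (yes/no) as a third minimisation factor within each subphenotype. Name it among the covariates of the adjusted model reported at adaptive and final analyses, since adjustment rather than balance recovers most of the power. If the statistical analysis plan already names it as a strong prognostic variable, that half is done. The factor would also help balance the population not intubated at baseline that 9.6 uses for the progression endpoint.

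Cost: one more field to enter and validate, a configuration change, and an unadjusted trigger that is slightly conservative. Moving the trigger itself to the adjusted POR is a valid alternative, but it changes the decision rule and would need new simulations.

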6.4 Visit Schedule

	Baseline (24 hours pre randomisation)	Day 0 (post randomisation)	D2	D6	Up to D28	Hosp D/C	D90	D180	D365
Screening	Х								
Informed Consent	Patient / PerLR / ProLR will be obtained initially. Retrospective patient consent will be obtained when the patient has recovered capacity to consent.								
Inclusion / Exclusion criteria	Х								
Phenotyping	X								
Randomisation	Х								
Research samples	Х		Χ	Х					
Intervention administration					Х				
Baseline data	X								
Data collection / follow up		X	X	Х	X	X	Χ	X	X
Physical function (SPPB)						Х			
MOCA						Χ	Χ	Χ	
Data collection in ICU (up to day 90 max)							X		
Vital status							Х		
Data collection in hospital (up to day 90 max)							Х		
EQ-5D-5L							Х	Х	
HADS							Χ	Х	
Social and Wellbeing (SF- 36)							X	Х	
Impact of Events Scale							Х	Х	
Care and wellbeing needs							Χ	Х	
Long-term follow-up									Х

Confidential Page 21 of 48

6.5 Treatment

Treatments within the trial will only be provided while the patients are in the ICU and will be provided and administered by local clinical staff.

Eligible patients will be randomised to usual care or one of the interventions for which they are eligible.

Each subphenotype will have its own control which will be usual care. Usual care will be directed by international treatment guidelines, such as the European Society of Intensive Care Medicine ARDS guidelines. Agreement to comply with these guidelines will be a condition for a site to participate in the trial to ensure standardised best practice usual care. We will collect and report key process measurements of usual care (e.g. compliance with protective lung ventilation and prone ventilation) with feedback and education for sites to achieve compliance with these guidelines if needed.

6.6 Follow-up

Patients will be followed up by the clinical research team daily whilst in ICU.

Once the patients have left ICU and been discharged to the ward, they will be followed up prior to hospital discharge. They will also be followed up by telephone or electronically 90 days, and 180 days after randomisation (+14 days). Survival status will be entered at 365 days. Where follow-up is not possible this will not be a protocol deviation.

6.7 Laboratory Evaluations

These will be intervention specific and described in the relevant intervention specific appendix

6.8 Research samples

Research samples will be collected as described in the sample handling manual. In summary there is a tiered approach to the collection of research samples and will include: -

- 1) blood samples for phenotyping, plasma, serum and RNA on the day of but prior to randomisation, day 2 and day 6.
- 2) blood samples for cell isolation on the day of randomisation and day 2.
- 3) tracheal aspirate samples on the day of randomisation, day 2 and day 6 (if intubated).
- 4) a nasopharyngeal swab on the day of randomisation and
- 5) a bronchoalveolar lavage sample in selected sites on the day of randomisation and day 2.

Details of the processing, handling and shipping are provided in the sample handling manual. The samples will be sent to a regional central laboratory for storage and analysis to understand the mechanism of effect of the interventions and heterogeneity of treatment effect as well as use in ethically approved studies.

Confidential Page 22 of 48

If resources prevent collection of the research samples this is not a protocol deviation.

